7.7 Acute Allergic Reaction

Oral antihistamines (e.g., cetirizine, levocetirizine) and/or topical corticosteroids may provide symptomatic relief but effectiveness of these measures has not been established. If treatment with systemic corticosteroids for longer than 24 hours would be required for an acute systemic allergic reaction, the study drugs need to be permanently discontinued.

Management of acute allergic reactions will take into account the protocol-defined procedures outlined in Table 7-2.

Table 7-2. Guidelines for Subjects Developing Allergic Reactions

WHO Toxicity Grade	Definitions	Investigator Action
Grade 1	Pruritus suggestive of an allergic reaction without rash	May continue study drugs or have their study drugs discontinued at the investigator's discretion.
Grade 2	Localized urticaria	May continue study drugs or have their study drugs discontinued at the investigator's discretion. Rechallenge is not allowed.
Grade 3	Generalized urticaria or angioedema	Permanently discontinue study drugs.
Grade 4	Anaphylaxis	Permanently discontinue study drugs.

Grade 1 (Pruritus Suggestive of an Allergic Reaction Without Rash)

Subjects may continue the intake of study drugs or have their study drugs discontinued at the investigator's discretion. Close clinical follow up is recommended to monitor for any progression of the AE. Subjects should be advised to contact the investigator immediately if there is any worsening of symptoms.

Grade 2 (Localized Urticaria)

Subjects may continue the intake of study drugs or have their study drugs discontinued at the investigator's discretion. Close clinical follow up is recommended to monitor for any progression of the AE. Subjects should be advised to contact the investigator immediately if there is any worsening of symptoms, in which case the subject will permanently discontinue the study drugs. Rechallenge is not allowed.

Grade 3 (Generalized Urticaria, Angioedema) and Grade 4 (Anaphylaxis)

Subjects will immediately and permanently discontinue the intake of study drugs. Rechallenge is not allowed. Subjects will be treated as clinically appropriate and should be followed until resolution of the AE.

7.8 Liver Function Tests

Liver chemistry management criteria have been designed to ensure subject safety. When subjects meet the liver chemistry threshold criteria, the subject's clinical case should be carefully reviewed with the medical monitor, additional testing performed, and the subject monitored until liver chemistries resolve, stabilize, or return to baseline values.

In situations requiring additional liver chemistry monitoring, every attempt should be made to obtain the following after discussion with the medical monitor:

Viral hepatitis serology including:

- Hepatitis A immunoglobulin M (IgM) antibody
 - HBsAg and hepatitis B core antigen IgM antibody
 - HCV RNA
 - Cytomegalovirus IgM antibody
 - Epstein-Barr viral capsid antigen IgM antibody (or if unavailable, obtain heterophile antibody or monospot testing)
 - Hepatitis E IgM antibody
- Blood samples for study medication PK analysis. If study treatment is discontinued, blood samples should be obtained within 2 days of the last dose of study drug. Record the date/time of the PK blood sample draw and the date/time of the last dose of the study drug before blood sample draw in the CRF. If the date or time of the last dose is unclear, provide the subject's best approximation. If the date/time of the last dose cannot be approximated OR a PK sample cannot be collected in the time period indicated above, do

not obtain the PK samples. Instructions for sample handling and shipping are in the Laboratory Manual.

- Serum creatine phosphokinase and lactate dehydrogenase
- If total bilirubin $\geq 2 \times$ ULN, fractionated bilirubin
- Complete blood count with differential to assess eosinophilia
- Record the appearance or worsening of clinical symptoms of hepatitis, or hypersensitivity, such as fatigue, nausea, vomiting, right upper quadrant pain or tenderness, fever rash or eosinophilia as relevant on the CRF
- Record use of concomitant medications, acetaminophen, herbal remedies, other OTC medications, or putative hepatotoxins, on the CRF
- Record alcohol use on the liver event alcohol intake page of the CRF

The following are required for subjects who meet the ALT and bilirubin management criteria but are optional for other abnormal liver chemistries and should be discussed with the medical monitor:

- Antinuclear antibody, antismooth muscle antibody, and type 1 anti-liver/kidney microsomal antibodies
- Serum acetaminophen adduct assay (quantifies potential acetaminophen contribution to liver injury, detectable by high-performance liquid chromatography assay more than 1 week following acetaminophen use) ([James et al. 2009](#))
- Liver imaging (ultrasound, magnetic resonance, or computed tomography) to evaluate liver disease

7.9 ALT, AST, and Bilirubin Elevations

Although an AST and ALT elevation of up to Grade 3 is common in chronic HCV infection due to disease activity, treatment-emergent changes from baseline in ALT and AST levels should be carefully evaluated and closely monitored, with unscheduled study visits if needed. Increases in bilirubin (both direct and indirect) have been observed during the first weeks of SMV therapy. These bilirubin elevations are caused by a benign competitive inhibition of biliary transporter systems in hepatocytes. Bilirubin elevations following initiation of SMV therapy are typically not associated with increases in ALT or AST levels and rapidly resolve after completion of SMV treatment. Bilirubin elevations have been observed to a much lesser extent with direct-acting antiviral regimens where SMV is administered without RBV compared to when it is administered with RBV.¹⁶

Management of treatment-emergent AST, ALT and/or bilirubin elevations will take into account the protocol-defined procedures outlined in Table 7-3, [Table 7-4](#), and [Table 7-5](#).

Table 7-3. Treatment-Emergent Grade 1 to Grade 4 ALT or AST Elevation and Grade 1 to Grade 4 Total Bilirubin Elevation

WHO Toxicity Grade	AST or ALT, Ranges	Total Bilirubin, Ranges
Grade 1	≥ 1.25 to $\leq 2.5 \times$ ULN	≥ 1.1 to $\leq 1.5 \times$ ULN
Grade 2	> 2.5 to $\leq 5.0 \times$ ULN	> 1.5 to $\leq 2.5 \times$ ULN
Grade 3	> 5.0 to $\leq 10.0 \times$ ULN	> 2.5 to $\leq 5.0 \times$ ULN
Grade 4	$> 10.0 \times$ ULN	$> 5.0 \times$ ULN

Subjects may continue the intake of study drugs at the investigator's discretion in case of Grade 1 and 2 increases in ALT and/or AST and/or Grade 1, 2 and 3 increases in bilirubin levels. In case of a Grade 3 ALT and/or AST increase or if a Grade 4 ALT and/or AST $\leq 2 \times$ the baseline value, this laboratory abnormality must be judged by the investigator to be either "not related" or "doubtfully related" to the study drugs in order to continue the intake of study drugs, in which case the intake of study drugs may be continued upon agreement with the Sponsor. In subjects who continue the study drugs, close clinical follow up is recommended to monitor for any progressive increases.

If a Grade 4 ALT and/or AST value is > 2 times the baseline value, a confirmatory measurement should be performed preferably within 72 hours after receipt of the results at the study site. If the Grade 4 value is confirmed to be > 2 times the baseline value, the study drugs should be discontinued (Table 7-4).

In case of a Grade 4 bilirubin value, subjects should have a confirmatory measurement within 72 hours after receipt of the results. If the Grade 4 value is confirmed but not considered a sign of worsening liver disease, or if there is an identifiable cause for the value (e.g., hereditary hyperbilirubinemia [Gilbert's syndrome] or concomitant medication associated event), subjects may continue the study drugs or have SMV discontinued while ODV and AL-335 can be continued at the investigator's discretion (Table 7-5). Subjects who continue the study drugs should be carefully evaluated and close follow up is recommended to monitor for progressive increase in bilirubin levels. If the Grade 4 value is confirmed and is considered a sign of worsening liver disease, or if there is no identifiable explanation for the confirmed value, all study drugs should be discontinued.

For concurrent Grade 4 ALT and/or AST elevations $> 2 \times$ the baseline value and Grade 4 bilirubin values, subjects should have a confirmatory measurement within 72 hours after receipt of the results. In case of confirmed Grade 4 elevations, the study drugs should be discontinued.

Subjects should be followed until return to predose baseline value or stabilization of ALT, AST and/or bilirubin elevation.

Table 7-4. Guidelines for Subjects Developing ALT and/or AST Elevations

WHO Toxicity Grade	Ranges	Investigator Action
Grade 1	≥ 1.25 to $\leq 2.5 \times$ ULN	May continue intake of study drugs at the investigator's discretion. Monitor for progressive increase in ALT and/or AST levels
Grade 2	> 2.5 to $\leq 5.0 \times$ ULN	May continue intake of study drugs at the investigator's discretion. Monitor for progressive increase in ALT and/or AST levels
Grade 3	> 5.0 to $\leq 10.0 \times$ ULN	In order to continue the study drugs, in case of a Grade 3 ALT and/or AST increase, this laboratory abnormality should be considered "not related" or "doubtfully related" to the study drugs. Study drugs may be continued upon agreement with the Sponsor. May continue study drugs at the investigator's discretion (upon agreement with the Sponsor) if value is $\leq 2 \times$ the baseline value and the event is considered "not related" or "doubtfully related" to study drugs. Subjects who continue should be carefully evaluated and close follow up is recommended to monitor for progressive increase in ALT and/or AST levels.
Grade 4	$> 10.0 \times$ ULN	If the Grade 4 ALT and/or AST value is $> 2 \times$ the baseline value, a confirmatory measurement should be performed within 72 hours after receipt of the results. If the value is confirmed, all study drugs should be discontinued.

NOTE:

Any significant ALT flare, defined as

- 1) ALT of $> 2 \times$ ULN AND $> 2 \times$ the lowest value during the study

OR

- 2) any treatment emergent grade 3 ALT elevation ($> 5 \times$ ULN)

will trigger a thorough clinical work-up of the case by the investigator. This evaluation should include the assessment of serum HBV-DNA (mandatory in subjects that are anti-HBc ab positive at screening or baseline). If HBV reactivation is confirmed, then appropriate treatment for HBV should be started if clinically appropriate.

Table 7-5. Guidelines for Subjects Developing Bilirubin Elevations

WHO Toxicity Grade	Ranges	Investigator Action
Grade 1	≥ 1.1 to $\leq 1.5 \times$ ULN	May continue intake of study drugs at the investigator's discretion. Monitor for progressive increase in bilirubin levels.
Grade 2	> 1.5 to $\leq 2.5 \times$ ULN	May continue intake of study drugs at the investigator's discretion. Monitor for progressive increase in bilirubin levels.
Grade 3	> 2.5 to $\leq 5.0 \times$ ULN	May continue intake of study drugs at the investigator's discretion. Monitor for progressive increase in bilirubin levels.
Grade 4	$> 5.0 \times$ ULN	
A confirmatory measurement should be performed within 72 hours after receipt of the results. If the value is confirmed and:
 
 Not considered a sign of worsening liver disease, or if there is an identifiable cause ^a for the confirmed value, subjects may continue study drugs or have SMV discontinued while ODV and AL-335 can be continued at the investigator's discretion. ^b Considered a sign of worsening liver disease, or if there is no identifiable explanation for the confirmed value, all study drugs should be discontinued. 
Monitor for progressive increase in bilirubin levels

a. For example, hereditary hyperbilirubinemia (Gilbert's syndrome) or concomitant medication associated event.

b. Monotherapy with any of the study drugs is not allowed.

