4.6.1 Subject Treatment Discontinuation Criteria

If a subject's study drug treatment must be discontinued before the end of the treatment regimen, this will not result in automatic withdrawal of the subject from the study.

A subject's study drug treatment (AL-335, SMV and ODV) must be permanently discontinued if:

- The investigator believes that for safety reasons (e.g., AE), it is in the best interest of the subject to discontinue study drug treatment.
- The subject becomes pregnant.
- The subject has evidence of muscle injury (Section 7.5.1) or cardiac toxicity (Section 7.5.2 and 7.5.3).
- The subject has a Grade 4 rash; see Section 7.6.
- The subject has a Grade 3 or 4 allergic reaction; see Section 7.7.
- The subject has a confirmed Grade 4 ALT and/or AST value that is $>2\times$ the baseline value; see Section 7.9.
- The subject has a confirmed Grade 4 bilirubin value which is considered a sign of worsening liver disease, or for which there is no identifiable explanation; see Sections 7.8 and 7.9.
- The subject has severe worsening of hepatic disease.
- The subject has a confirmed diagnosis of pancreatitis.
- The subject has a Grade 4 AE or laboratory abnormality at least possibly related to 1 of the study drugs and which is considered clinically significant (laboratory abnormalities only).
- The subject requires treatment with any of the medications reported on the list of disallowed medications; see Section 5.12.
- The subject experiences inadequate virologic response or viral breakthrough (refer to Definitions)
- An event occurs which triggers the study treatment stopping criteria (Section 4.7.1)

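### For a confirmed Grade 4 bilirubin, Section 7.9 and Table 7-5 permit dosing to continue in two situations where Section 4.6.1 requires permanent discontinuation; changing 'or' to 'and' in the continue condition removes the conflict

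*Protocol*

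**What the plan says.** Three places in the Protocol govern a confirmed Grade 4 total bilirubin (above 5 times the upper limit of normal in Tables 7-3 and 7-5).

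- **Section 7.9, text.** The continue condition reads "If the Grade 4 value is confirmed but not considered a sign of worsening liver disease, or if there is an identifiable cause". When it is met, the subject may stay on all drugs, or may stop simeprevir alone and stay on the other two, as the investigator decides. The paragraph ends with the stop rule, for a confirmed value that signals worsening "or if there is no identifiable explanation for the confirmed value, all study drugs should be discontinued".
- **Table 7-5, Grade 4 row.** The first bullet permits continuation when the confirmed value is "Not considered a sign of worsening liver disease, or if there is an identifiable cause". The second bullet is the stop rule: "Considered a sign of worsening liver disease, or if there is no identifiable explanation for the confirmed value, all study drugs should be discontinued".
- **Section 4.6.1.** The lead-in says that "study drug treatment (AL-335, SMV and ODV) must be permanently discontinued if" any listed criterion is met. One of these is a "confirmed Grade 4 bilirubin value which is considered a sign of worsening liver disease, or for which there is no identifiable explanation". The item then refers the reader to Sections 7.8 and 7.9.

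No sentence in Section 7.9 or Table 7-5 says which branch takes precedence when both apply.

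**The concern.** The two branches are evidently meant to be opposites, but both are joined by 'or'. The opposite of 'worsening or unexplained' is 'not worsening and explained'; the continue branch says 'not worsening or explained', which is wider. Some subjects therefore fall under both branches, and the continue branch permits dosing that Section 4.6.1 forbids.

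What is at stake is compliance with a mandatory safety stop in a study whose primary objective is safety. Cohorts 6 to 12 are all in subjects with compensated cirrhosis, where a bilirubin above 5 times the upper limit of normal matters most. A site that works from the first bullet of Table 7-5 could keep dosing a subject whom Section 4.6.1 says must come off all three drugs, and up to 50 sites may apply the rule. No endpoint definition, analysis or sample size is affected.

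**Working it through.** The plan has no figure to reproduce; this is a check of decision logic.

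Inputs, all for a value already confirmed as Grade 4:

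- W = the value is considered a sign of worsening liver disease.
- E = a cause or explanation has been identified. The text says *cause* in the continue branch and *explanation* in the stop branch; I take them to mean the same thing.

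Conditions as written:

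- Continue (Section 7.9; Table 7-5, first bullet): not W **or** E
- Stop (Section 7.9; Table 7-5, second bullet): W **or** not E
- Mandatory stop (Section 4.6.1, bilirubin item): W **or** not E

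Corrected condition:

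- Continue: not W **and** E

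| W | E | Continue as written | Stop as written | 4.6.1 requires stop | Continue with 'and' |
|---|---|---|---|---|---|
| no | no | yes | yes | yes | no |
| no | yes | yes | no | no | yes |
| yes | no | no | yes | yes | no |
| yes | yes | yes | yes | yes | no |

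As written, continuation is permitted in 3 of 4 combinations and a stop is required in 3 of 4. Every combination meets at least one branch, so the overlap is 3 + 3 − 4 = 2: (a) not worsening and unexplained, and (b) worsening with a cause identified. Section 4.6.1 requires a stop in both.

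With 'and', continuation is permitted in 1 of 4 and a stop is required in 3 of 4. Since 1 + 3 = 4 with no combination in both columns, there are 0 overlaps and 0 gaps. By De Morgan's rule, not (W or not E) = (not W and E), so the corrected branch is the exact complement of the Section 4.6.1 bilirubin criterion in all 4 combinations.

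The other possible repair is to change the stop branch to W **and** not E. That also makes the branches complementary (continue 3, stop 1), but it disagrees with Section 4.6.1 in 2 of 4 combinations, namely (a) and (b). The continue branch is therefore the one to edit.

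**The case against.** The strongest reply is that the Protocol already resolves the conflict. Section 4.6.1 is mandatory, while the continue branch is a permission exercised at the investigator's discretion, in a table presented as guidance. A permission does not displace an obligation. The stop rule also stands in the same paragraph and the same table row, so a careful reader meets both. This stands, and it limits the point: a reader might infer that the Protocol leaves these subjects with no determinate answer, or without a mandatory stop. The documents do not support that. The Section 4.6.1 bilirubin item covers both overlap combinations. Other items there may add reasons to stop, such as "The subject has severe worsening of hepatic disease" or a "Grade 4 AE or laboratory abnormality at least possibly related to 1 of the study drugs and which is considered clinically significant".

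The reply does not make the continue text correct. Section 4.6.1 sends the investigator to Section 7.9, where the permissive branch comes first, and the reader has to work out that the stricter branch controls.

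A second reply is that few subjects will get there. Bilirubin rises in the Phase 3 simeprevir trials were mostly Grade 1 or 2 (Section 1.4.1). Entry excludes screening bilirubin of 1.5 mg/dL or more, apart from documented Gilbert's disease (Section 4.3). As of 6 February 2017, 123 subjects had been dosed and all 336 treatment-emergent events were mild or moderate. Apart from one case of PR prolongation, no clinically significant finding suggesting a safety concern, laboratory findings included, was reported (Section 1.2.1.2). That does not prove that no Grade 4 bilirubin occurred, but it gives no sign that the branch has been reached.

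Both overlap combinations are also narrow. For (a), the benign transporter mechanism of simeprevir described in Section 7.9 may often serve as the explanation. Cohorts 6 to 12 all include simeprevir, although later cohorts may not. For (b), worsening and a named cause will seldom coexist, but they can. The Protocol's own examples of a cause include a concomitant-medication event, and the note under Table 7-4 anticipates hepatitis B reactivation. The separate rule for concurrent elevations stops dosing only when ALT or AST is also Grade 4 and more than twice baseline.

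**Conclusion.** The point holds as a contradiction between permissive guidance and a mandatory safety rule, in 2 of 4 logical combinations. These are combinations of two judgements, not proportions of patients. The documents give no Grade 4 bilirubin rate, so no number of affected subjects can be estimated, and events are likely to be rare. Section 4.6.1 is correct as written and controls; the error lies only in the continue condition of Section 7.9 and Table 7-5.

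The conclusion rests on two readings: that *cause* and *explanation* are the same test, and that confirmation applies to both halves of the continue condition. Table 7-5 makes the second explicit by putting confirmation ahead of both bullets. The wording should be corrected, but nothing in the documents shows that a subject has been wrongly continued.

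**What to change.** In Section 7.9, reword the continue condition so that all three parts are required: the Grade 4 value is confirmed, it is not considered a sign of worsening liver disease, **and** there is an identifiable cause. Keep the existing examples of causes. Make the same change from 'or' to 'and' in the first Grade 4 bullet of Table 7-5. Leave the stop branch and Section 4.6.1 as they are.

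The cost is wording in two places, with no added data, visits or subjects. Under Section 11.0 an amendment needs ethics approval and, as appropriate, regulatory approval before it takes effect, so the change can reasonably be bundled with the next amendment.

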8.0 STUDY VARIABLES AND MEASUREMENTS

8.1 Safety Variables/Measurements

Safety evaluation will include AEs and SAEs, vital signs, laboratory tests (including hematology and serum chemistries), ECG, echocardiograms, physical examination, urinalysis, and pregnancy tests.

8.1.1 Adverse Events

Adverse events, including pretreatment events, will be recorded from the time of consent through the SVR24 visit. All AEs/SAEs will be coded using the *Medical Dictionary for Regulatory Activities (MedDRA)*.

8.1.2 Clinical Laboratory Measurements

Clinical laboratory variables, including hematology, serum chemistries, urinalysis, and pregnancy testing, will be assessed at screening. Hematology, serum chemistries, and pregnancy testing will be evaluated periodically during the study as indicated in this protocol. Local labs will be used for real time clinical decision making, while central labs will be used for purposes of the clinical database.

8.1.3 Prior and Concomitant Medications

Use of all medications and supportive therapy from within 30 days of the screening visit through study completion will be recorded. All concomitant medications will be mapped using the WHO Drug Dictionary.

8.2 Efficacy Variables/Measurements

HCV RNA will be measured in all subjects (Section 6.2.3).

The key efficacy variables include the proportion of subjects who achieve SVR demonstrated by sustaining HCV RNA <LLOQ 4, 8, 12, 18 and 24 weeks after the end of treatment (SVR4, SVR8, SVR12, SVR18 and SVR24), regardless of whether or not the subject completed the assigned treatment regimen.

The results will be presented by treatment group by means of descriptive statistics.

The SVR rates will also be presented by subgroups defined by baseline characteristics such as HCV genotype, prior HCV treatment, and IL-28B genotype status.

Additional efficacy variables to be analyzed include:

- The proportion of subjects who have relapse (i.e., who had <LLOQ HCV RNA at actual end of treatment (EOT) followed by \geq LLOQ HCV RNA after planned EOT)
- The proportion of subjects who achieve undetectable HCV RNA <LLOQ (undetectable) at Weeks 2, 4, 6, and 8 after the first dose of study drug
- Time to achieve HCV RNA <LLOQ and <LLOQ undetectable
- The proportion of subjects who have on treatment failure
- The proportion of subjects who achieve SVR12 by IL-28B genotype (CC or non-CC)

